Clinical Validation of the Aptitude Medical Systems Metrix COVID/Flu Test for Detection of SARS-CoV-2 and Influenza A/B in Point-of-Care and At-Home/Non-Laboratory Settings Protocol Version: 0

Protocol ID: TP-23-003

Protocol Title: Clinical Validation of the Aptitude Medical Systems Metrix COVID/Flu Test for

Detection of SARS-CoV-2 and Influenza A/B in Point-of-Care and Non-Laboratory

Settings

Protocol ID: TP-23-003

NCT06191393

Version 0

Date: 23 OCT 2023

Sponsor: Aptitude Medical Systems, Inc.

[name]

[name]

Sponsor Contact: [name]

Aptitude Medical Systems, Inc. Head of Scientific and Medical Affairs [contact]

[name]

[name]

CONFIDENTIALITY NOTICE:

The information contained in this document is proprietary and confidential. Any distribution, copying, or disclosure is strictly prohibited unless such disclosure is required by federal regulations or state law. Persons to whom the information is disclosed must know that it is confidential and that it may not be further disclosed by them.

The Metrix COVID/Flu Test is intended for 510(k)/De Novo submission. FOR INVESTIGATIONAL USE ONLY and has not been FDA cleared/market authorized The performance characteristics of this product have not been established.

Protocol ID: TP-23-003

1. Protocol Summary

Protocol Title	Clinical Validation of the Aptitude Medical Systems Metrix COVID/Flu Test for Detection of SARS-CoV-2 and Influenza A/B in Point-of-Care and At-Home/Non-Laboratory Settings	
Investigational Device(s)	Metrix COVID/Flu Test Metrix Reader (Gen 2)	
Primary Objective(s)	To evaluate the clinical performance (Positive Percent Agreement, Negative Percent Agreement, and 95% confidence intervals) of the Metrix COVID/Flu Test in detecting SARS-CoV-2, Influenza A, and Influenza B compared to an FDA-cleared comparator assay.	
Primary Endpoint(s)	For each target: • PPA ≥95% (lower bound 95% CI ≥85%) • NPA ≥98% (lower bound 95% CI ≥95%)	
Study Design and Procedures	This is a multi-site, prospective, cross-sectional study. Enrollment will occur in an "all-comers"/sequential manner after written informed consent (and/or verbal assent, in the case of minors) and confirmation of eligibility.	
	All standard-of-care specimens will be collected prior to any study specimens. Participants will be asked to complete a self-test (or assisted for those under 14 years) using the investigational devices. Participants will execute all steps necessary to complete the test, including result interpretation, without any guidance or aid from study coordinators.	
	After testing with the investigational devices, a healthcare professional will collect a nasopharyngeal swab specimen for comparator assay analysis by an external reference laboratory. Comparator results will not be provided to participants.	
	Results from the investigational device will not be used to make patient healthcare decisions. Healthcare management will be determined by the healthcare provider and their patient without any involvement of the Sponsor.	
Study Population	Individuals aged 2+ years with signs and symptoms of respiratory infection. Intended users of the investigational device include lay-users (OTC/home use) with no prior laboratory experience with the investigational device. Participants aged 14 years and up will perform self-testing and participants below 14 years will be assisted by an adult.	

Protocol ID: TP-23-003

Number of Participants	Enrollment and testing will continue until a minimum of 500 negative specimens, 50 positive SARS-CoV-2 specimens, 50 positive Flu A specimens, and 30 positive Flu B specimens are collected.	
Inclusion/Exclusion Criteria	 Inclusion Criteria: Participant or guardian understands and is able and willing to provide written informed consent, and assent where applicable, prior to study enrollment. Male or female aged 2 years or older Participant is currently exhibiting fever, or one or more symptoms of respiratory tract infection (such as, but not limited to, chills, cough, shortness of breath or difficulty breathing, fatigue, new loss of taste or smell, sore throat, congestion or runny nose, nausea or vomiting or diarrhea). Participant must still be exhibiting symptoms on the day of specimen collection. Participant or guardian agrees to read, and is able to read with understanding, the AN swab QRI prior to beginning the operation of each of the Metrix COVID/Flu Test. Participant or guardian is able and willing to contribute the required swab specimens for testing and understands and is able and willing to sign the study informed consent. Exclusion Criteria:	
	 Participant does not understand and/or is not able and willing to sign the study informed consent and/or assent. Participant or guardian is not able to comply with nasal swab collection requirements following the QRI. Participant has previously provided a specimen for the study. Participant is not able to tolerate specimen collection. Participant is currently undergoing antiviral treatment such as baloxavir marboxil (trade name Xofluza®), oseltamivir (Tamiflu®), zanamivir (Relenza®), and peramivir (Rapivab®). Participant is currently underoing, and/or has undergone within the past 30 days, treatment with prescription medication to treat novel Coronavirus SARS-CoV-2 infection, which may include but is not limited to Remdesivir (Veklury), Paxlovid, molnupiravir or receiving convalescent plasma therapy for SARS-CoV-2. Participants who have had a nasal wash or aspirate as part of their standard of care treatment on day of study visit prior to the study specimen collection. 	
Study Sites	The study will be conducted at a minimum of three investigational sites located within the United States. Additional sites may be added to the study to meet minimum subject/specimen enrollment requirements and geographic prevalence of respiratory virus	

Protocol ID: TP-23-003

	infections. This may include utilizing one or more investigational sites outside of the US (at which participants are required to be fluent in English), depending on enrollment needs and geographical/seasonal prevalence of respiratory virus infections. This study will be conducted in simulated home environments set up within or near clinical settings (e.g., urgent care clinics).
Study Duration	The study is to take place during the 2023 respiratory season. The estimated length of the specimen collection and testing phase is expected to be up to 24 weeks with an additional 2 to 3 weeks of study preparation and 2 weeks of final study closeout. Therefore, the total estimated study duration is up to 29 weeks. If the prevalence for any of the candidate analytes is low (such that enrollment targets are not met), the study may be extended into the next respiratory season to facilitate collection of additional specimens.

2. Reference Documents

1. Premarket Validation Recommendations for Developers of SARS-CoV-2 Molecular Single Analyte In Vitro Diagnostic Tests and Multi-Analyte Molecular Respiratory Panels that Include SARS-CoV-2 (Feb 2021)

3. Statistcal Analysis

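### Could a standard-of-care result known before the self-test bias the lay reading enough to need a change to the plan?

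*Combined protocol and SAP*

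**What the plan says.** Section 1 (Study Design and Procedures) sets the order of events. First, "All standard-of-care specimens will be collected prior to any study specimens". The self-test follows, and "Participants will execute all steps necessary to complete the test, including result interpretation, without any guidance or aid from study coordinators"; children under 14 are helped by an adult. A healthcare professional then takes a nasopharyngeal swab, which an external reference laboratory runs on the comparator assay. On masking, the section says "Comparator results will not be provided to participants". On clinical care, it says "Healthcare management will be determined by the healthcare provider and their patient without any involvement of the Sponsor".

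The investigational devices listed in Section 1 include a dedicated Metrix Reader. Its display is not described. The exclusions cover some people likely to know a diagnosis, for example where "Participant is currently undergoing antiviral treatment such as baloxavir marboxil" applies, and those treated for COVID now or in the past 30 days. They do not cover an untreated person who has been told a result.

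Section 3.1 gives PPA and NPA per target with Wilson 95% intervals, and adds demographics, the invalid rate and, if applicable, performance by days from symptom onset. Prior knowledge of a result is not among the reported items. The document includes no case report form, so what is recorded, as opposed to reported, cannot be judged.

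**The concern.** The primary endpoints depend on what a lay person reads and reports. Participants have symptoms and test themselves in or near clinics, where their own care runs in parallel. If a routine SARS-CoV-2 or influenza result came back first, the reader could know the likely answer before looking at the study device. Where that result matched the comparator, a would-be misreading might be put right and both PPA and NPA would be flattered. A wrong routine result could pull the other way.

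The stakes look high because margins are thin at the minimum counts. With 50 positives the PPA criterion tolerates two misses; with 30 Flu B positives it tolerates none. A single altered reading could therefore decide a target.

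**Working it through.** **Inputs from the document.** Minimum counts: 500 negatives, 50 SARS-CoV-2 positives, 50 Flu A positives, 30 Flu B positives (Section 1, Number of Participants). Success: PPA at least 95% with lower limit at least 85%; NPA at least 98% with lower limit at least 95% (Section 3.2). Intervals: two-sided 95% Wilson (Section 3.1). The plan gives no power figure or assumed true agreement, so there is no stated figure to reproduce.

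**Step 1: the pass boundaries.** Wilson lower limit = [p + z²/2n − z√(p(1−p)/n + z²/4n²)] / (1 + z²/n), z = 1.96.

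| Result | Estimate | Lower limit | Verdict |
|---|---|---|---|
| 48/50 | 96.0% | 86.5% | pass |
| 47/50 | 94.0% | 83.8% | fail |
| 30/30 | 100% | 88.6% | pass |
| 29/30 | 96.7% | 83.3% | fail on the limit |
| 490/500 | 98.0% | 96.4% | pass |
| 489/500 | 97.8% | 96.1% | fail on the estimate |

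**Step 2: what the bias needs.** Let r be the share of disagreements that prior knowledge removes. Then

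r = (share who know a concordant result) × (share of disagreements due to misreading rather than assay or sampling) × (chance that knowledge corrects the reading).

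The document gives none of these. I assume true PPA 95%, true NPA 98% and correction always successful, which is the worst case for the third factor. Observed PPA = 1 − 0.05(1 − r); observed NPA = 1 − 0.02(1 − r). Pass probabilities are exact binomial: P(X ≥ 48 of 50), PPA^30, and P(X ≥ 490 of 500).

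| Aware × misread (assumed) | r | n = 50 | Flu B, n = 30 | NPA, n = 500 |
|---|---|---|---|---|
| none | 0 | 0.541 | 0.215 | 0.583 |
| 10% × 10% | 1% | 0.547 | 0.218 | 0.596 |
| 20% × 10% | 2% | 0.554 | 0.222 | 0.608 |
| 25% × 20% | 5% | 0.574 | 0.232 | 0.646 |
| 30% × 20% | 6% | 0.581 | 0.236 | 0.658 |
| 80% × 50% | 40% | 0.811 | 0.401 | 0.958 |

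The last row shows what a large effect would require: four in five readers already informed, and half of all disagreements being misreadings.

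At r = 2% the expected number of changed readings is 50 × 0.05 × 0.02 = 0.05, 30 × 0.05 × 0.02 = 0.03 and 500 × 0.02 × 0.02 = 0.2.

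**Step 3: what a split by prior knowledge could show.** Expected false negatives are 50 × 0.05 = 2.5 and 30 × 0.05 = 1.5; expected false positives are 500 × 0.02 = 10. With 20% aware and no bias, the aware group would hold 0.5, 0.3 and 2.0 of these. If 10% of disagreements are misreadings and all are corrected, it would hold 0.45, 0.27 and 1.8. No table of this size can tell those apart.

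Precision in the unaware Flu B group also falls quickly. The lower limit is 86.2% at 24/24 and 79.8% at 23/24. It is 85.1% at 22/22 but 84.5% at 21/21, so below 22 unaware positives even perfect agreement misses 85%. Aware participants may also differ in severity or viral load, which would confound the comparison.

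**The case for a change.** The best case for acting is that the gap is real and cheap to close. The plan masks one result and is silent on another that could reach the reader. The exclusions do not catch an untreated person who knows a result. If awareness is not noted at the time, it is hard to reconstruct. One case report form item and one descriptive table would cost little, and uncertainty about the size of the effect is itself a reason to look.

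Part of this stands: the document does not mask routine results and names no analysis by prior knowledge. The rest is weaker. That one reading can decide a target follows from the minimum counts and success limits, and holds for any source of a discordant result; it is not evidence about prior knowledge. The protections already in place also narrow the issue. The comparator swab is taken after the self-test, analysed externally and withheld. Staff may not help with interpretation, which already largely keeps them from discussing a clinical result during the reading. The proposed table, by the arithmetic above, would seldom answer the question it was added to answer.

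**Conclusion.** No change to the plan is needed. The document shows a possible pathway but no bias: each link, from what routine testing covers to whether knowledge could alter a reading on this system, is unstated. With the components set at 1% to 6% combined, the pass probability rises by 0.006 to 0.040 with 50 positives, by 0.003 to 0.021 with 30 Flu B positives, and by 0.013 to 0.075 for NPA with 500 negatives. If the reader leaves little to interpret, the effect is near zero. These figures assume the minimum counts, true agreement of 95% and 98%, and a routine result that matches the comparator. They would be larger if many participants were informed and misreading were common.

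An analysis by prior knowledge would leave the primary population, estimates and success rule as they are, and could not separate reader bias from chance. The sponsor may still choose to note on the case report form whether a result was known beforehand. That is good record-keeping, and the stated analysis is sound without it.

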3.1. Clinical Performance Analysis

For each target, the following analysis will be performed to obtain a measure of clinical performance of the Metrix COVID/Flu Test versus the FDA-cleared comparator assay. Positive Percent Agreement (PPA) and Negative Percent Agreement (NPA) will be calculated as shown below. The PPA and NPA will be presented in separate 2x2 tables for each target with comparator vs investigational test (test device).

		Comparator Test		
		Positive	Negative	
Test	Positive	А	В	
Device	Negative	С	D	

Positive percent agreement = $100\% \times A/(A+C)$ Negative percent agreement = $100\% \times D/(B+D)$

The two-sided 95% Confidence Interval (CI) will be calculated using the Wilson Score method.

The study will also report participant demographics, percentage of invalid test results and investigational test performance on days from symptom onset (if applicable).

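### Do the entry criteria need to screen for prior experience with the test, and does naming point-of-care in the title need a bridge?

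*Combined protocol and SAP*

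**What the plan says.** The Study Population row of the Protocol Summary describes the users: "Intended users of the investigational device include lay-users (OTC/home use) with no prior laboratory experience with the investigational device". The same row has those aged 14 and over test themselves, while "participants below 14 years will be assisted by an adult". The Study Design row says that study coordinators give no help.

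Two criteria touch on the operator. One inclusion criterion begins "Participant or guardian agrees to read, and is able to read with understanding, the AN swab QRI", and one exclusion applies where "Participant or guardian is not able to comply with nasal swab collection requirements following the QRI". Both concern reading the instructions and taking the swab. The only criterion that bears on earlier contact with the test is the exclusion "Participant has previously provided a specimen for the study".

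On reporting, section 3.1 says: "The study will also report participant demographics, percentage of invalid test results and investigational test performance on days from symptom onset". Operator experience is not listed.

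On setting, the title in the Protocol Summary refers to "Detection of SARS-CoV-2 and Influenza A/B in Point-of-Care and At-Home/Non-Laboratory Settings". The Study Sites row places the work in simulated homes at or near clinics. The healthcare professional's stated task is the comparator nasopharyngeal swab. The primary objective is to evaluate the performance "of the Metrix COVID/Flu Test in detecting SARS-CoV-2, Influenza A, and Influenza B compared to an FDA-cleared comparator assay"; it names neither user nor setting.

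**The concern.** A study meant to support over-the-counter use should be run by people like the eventual users. The protocol describes those people, but nothing at screening checks that the operators match the description.

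The repeat bar leaves an opening. A parent can assist one child and then a sibling, or be tested and then assist a child, without breaching any criterion. Someone with laboratory or healthcare training can also enter an all-comers sample. If practised operators make fewer errors, PPA and NPA would be flattered and the invalid rate would look too low. With no operator experience listed for reporting, the analysis might be unable to separate those tests afterwards.

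The title adds a second worry. It names point-of-care, but no trained operator runs the Metrix test and no argument carries lay-user results over to that setting. A point-of-care claim would then rest on an unstated extrapolation.

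**Working it through.** **1. Is the description an entry rule?** The five inclusion criteria cover consent, age, symptoms, reading the instructions and willingness to give swabs. The seven exclusions cover consent, swab compliance, an earlier specimen, tolerance of collection, influenza antivirals, SARS-CoV-2 treatment, and nasal wash or aspirate. None screens experience or training. However, the sentence says that intended users include such lay users, which describes the intended users and is not exhaustive. It also speaks of laboratory experience with this device. That phrase is ambiguous, and an adult who helped one child in a simulated home does not clearly have such experience. No passage limits the results to first-time use.

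**2. Who could be experienced?** The title page says that the device is investigational and not market authorized, so use outside the study should be rare. The repeat bar removes participants who have already given a specimen. This leaves mainly adults who assist more than once or assist after being tested. Trained people may also enter, but nothing in the protocol says that they should be kept out.

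**3. How much could it matter?** The plan gives no figure to reproduce: it states no experienced share and no difference in PPA. The inputs below are therefore assumptions, except the specimen minima (50, 50 and 30) and the success criterion (PPA at least 95%, Wilson lower bound at least 85%).

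Pass lines at the minimum numbers:

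| Result | PPA | Wilson 95% lower bound | Meets criterion |
|---|---|---|---|
| 47/50 | 94.0% | 83.8% | No |
| 48/50 | 96.0% | 86.5% | Yes |
| 29/30 | 96.7% | 83.3% | No |
| 30/30 | 100% | 88.6% | Yes |

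With experienced share s, pooled PPA = lay PPA × (1 − s) + experienced PPA × s, so the shift is s × (experienced − lay). The smallest case is 0.01 × 2 = 0.02 points and the largest is 0.05 × 6 = 0.30 points.

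The chance of passing is P(X ≥ 48) with n = 50 for SARS-CoV-2 and Flu A, and p³⁰ for Flu B:

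| Lay / experienced PPA | s | Pooled PPA | P(at least 48/50) | P(30/30) |
|---|---|---|---|---|
| 93% / 99% | 0 | 93.00% | 31.1% | 11.3% |
| 93% / 99% | 1% | 93.06% | 31.7% | 11.6% |
| 93% / 99% | 5% | 93.30% | 34.0% | 12.5% |
| 97% / 99% | 0 | 97.00% | 81.1% | 40.1% |
| 97% / 99% | 1% | 97.02% | 81.3% | 40.3% |
| 97% / 99% | 5% | 97.10% | 82.3% | 41.4% |

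The largest change is 34.0 − 31.1 = 2.9 percentage points. To raise P(at least 48/50) by 5 points, the share would have to be about 8% (93%/99%) or 21% (97%/99%).

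**4. Would a sensitivity analysis help?** At shares of 1% to 5%, leaving out experienced operators would remove 0.5 to 2.5 of 50 positives, or 0.3 to 1.5 of 30. Such an analysis could show almost nothing.

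**5. Point-of-care.** The documents contain no point-of-care endpoint, operator group, analysis or conclusion. The wording is in the title only, and it changes no calculation of PPA or NPA.

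**The case for a change.** The strongest case for acting is that the gap is real and cheap to close. The Study Population row is the only statement of whom the results represent, and nothing ties the enrolled operators to it. The sibling route operates inside the study, so the device's unauthorized status does not remove it. Experience that is not recorded cannot be examined later, and one screening question with one recorded field would settle the matter. A study intended for a 510(k)/De Novo submission might also be expected to say which setting its results support.

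Much of this stands as description. No criterion screens the operator, the repeat bar does not reach the assisting adult, and no bridge to point-of-care is written down. The 1% to 5% share is also an assumption. At 20% experienced operators, with 93% and 99% PPA, P(at least 48/50) would be 44% rather than 31%. But nothing in the documents points to a share of that size, and the repeat bar and investigational status point the other way. Keeping trained people out of an all-comers sample is a design preference that the protocol does not adopt. For point-of-care, lay results may well be conservative for trained staff, and any bridging argument may belong in the submission, which is not available here.

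**Conclusion.** No change to the plan is needed. The protocol leaves a detail unstated, but following it as written still gives a sound PPA, NPA and invalid rate for all-comers testing without help from study staff.

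The likely distortion is negligible: 0.02 to 0.30 points of PPA under the assumed shares and gaps, against 100/50 = 2 points for one specimen at n = 50, and at most about 3 percentage points in the chance of passing. This rests on experienced operators being few. The documents make that plausible but do not measure it. A share well above 5% combined with a large performance gap would alter the judgement.

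The point-of-care phrase is a matter of title wording. Those who report the study can describe the setting as it was, lay use in a simulated home, without amending the endpoints, sample size or analysis.

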3.1. Clinical Performance Analysis

For each target, the following analysis will be performed to obtain a measure of clinical performance of the Metrix COVID/Flu Test versus the FDA-cleared comparator assay. Positive Percent Agreement (PPA) and Negative Percent Agreement (NPA) will be calculated as shown below. The PPA and NPA will be presented in separate 2x2 tables for each target with comparator vs investigational test (test device).

		Comparator Test		
		Positive	Negative	
Test	Positive	А	В	
Device	Negative	С	D	

Positive percent agreement = $100\% \times A/(A+C)$ Negative percent agreement = $100\% \times D/(B+D)$

The two-sided 95% Confidence Interval (CI) will be calculated using the Wilson Score method.

The study will also report participant demographics, percentage of invalid test results and investigational test performance on days from symptom onset (if applicable).

